***Secondary outcomes:***

For secondary and exploratory quantitative outcomes, only a descriptive analysis will be done by reporting the mean, median and range values as well as plotting the values using spaghetti plots showing the change from control to experimental period (by indicated the sequence of treatment using dedicated colors). We will also report the standardized differences (Hedges'g) calculated from the within-patient's differences (E1-S2 and E2-S1) as effect size (calculated on rank transformed data). The frequency of adverse events during the 4 weeks of treatment period will be reported in each treatment group without statistical comparison.

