### ***Phase II study:***

The primary objective is to determine the efficacy (superiority) of administration of intracerebroventricular (ICV) dopamine in combination of oral L-dopa at optimized dose versus usual optimized oral medical treatment in combination with ICV Placebo for improving PTO in patients with Parkinson's disease in the stage of severe motor and non-motor complications related to L-dopa.

Secondary objectives are:

1) to assess the efficacy of administration of ICV dopamine in combination of oral L-dopa at optimized dose versus usual optimized oral medical treatment in combination with ICV Placebo on:

- motor aspects
- cognitive-behavioural aspects: drowsiness, anxiety, depression, apathy, sleep, hallucinations
- cognition and psychiatric assessment
- quality of life
- general condition

2) To assess the tolerance of administration of intracerebroventricular dopamine versus usual optimized oral medical treatment alone

- 3) To assess the psychiatric tolerance of administration of intracerebroventricular dopamine versus usual optimized oral medical treatment alone

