In second efficacy phase II, 20 patients will be enrolled after terminating the titration phase I without complications and randomized in two groups according to cross-over design of 2 treatment periods of 4 weeks separated by a therapeutic switch carried out in the hospital. The previous treatment will be stopped at the end of period 1 and replaced by the new treatment, after 3 weeks of washout. During the 2 treatment periods and washout period, the patients will be treated by oral L-dopa at optimized dose. In summary, patients will be randomized into two groups according to the following treatment sequences:

- group 1 (n=10): period 1(ICV dopamine treatment + oral L-dopa at optimized dose) vs. period 2 (oral treatment at optimized dose + ICV Placebo treatment)
- group 2 (n=10): period 1: (oral treatment optimized + ICV Placebo treatment) vs. period 2 (ICV dopamine treatment + oral L-dopa at optimized dose)

At the end of phase II, all patients are invited to continue to use ICV dopamine treatment over the long term with the dose that allows satisfactory motor control (less than 1 hour of moderate or severe off per day and less than half an hour of dyskinesia) with or without a minimal residual dose of oral dopaminergic therapy.

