## 2.2 Randomisation

For the phase II part of the DIVE-1 study, patients are randomized in 2 treatment sequences according to a balanced plan (1:1) by using a randomization list generated by computer and provided by an independent statistician of CHU of LILLE. The randomization list will be implemented into the eCRF developed with Clinsight software. Patients will be randomized as soon as possible after having completed the phase I part of study (patients reached, at this time, a balanced titration established within 9 weeks).

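### Phase II adverse events are counted by treatment within the 4-week periods only, so events soon after ICV dopamine stops fall under control in one sequence and under no treatment in the other

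*SAP*

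**What the plan says.** Four parts of the SAP bear on this point.

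- **Objective.** Section 1.3 makes tolerance a comparative secondary objective of phase II: "To assess the tolerance of administration of intracerebroventricular dopamine versus usual optimized oral medical treatment alone".
- **Entry.** Section 2.1 states that "20 patients will be enrolled after terminating the titration phase I without complications and randomized in two groups according to cross-over design". Section 2.2 adds that "Patients will be randomized as soon as possible after having completed the phase I part of study", and describes their state then: "patients reached, at this time, a balanced titration established within 9 weeks".
- **Washout.** Section 2.1 places one washout, between the periods: "The previous treatment will be stopped at the end of period 1 and replaced by the new treatment, after 3 weeks of washout". It again speaks of a single washout when it describes background therapy: "During the 2 treatment periods and washout period, the patients will be treated by oral L-dopa at optimized dose". For group 2 (sequence S-E) the order is "period 1: (oral treatment optimized + ICV Placebo treatment) vs. period 2 (ICV dopamine treatment + oral L-dopa at optimized dose". No washout is stated before period 1.
- **Counting rule.** Under Secondary outcomes in section 5.2.2: "The frequency of adverse events during the 4 weeks of treatment period will be reported in each treatment group without statistical comparison". For quantitative outcomes the same paragraph asks for sequence to be marked on the plots. The adverse-event sentence asks for neither sequence nor period. It has no rule for events that begin in the washout or soon after ICV dopamine is stopped.

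**The concern.** The two control periods do not have the same history. S2 (control in E-S) begins after 3 weeks without ICV dopamine. S1 (control in S-E) begins after titration, with no separation stated in the SAP. A late effect of ICV dopamine, or an effect of stopping it, would be treated differently in the two sequences. In S-E it falls in a control window. In E-S it falls in the washout, outside both 4-week windows, and is tabulated under neither treatment. In neither sequence is it counted against ICV dopamine. Titration events that run on into E1 do not offset this, because they are dopamine events and are counted as such.

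At stake is how the tolerance objective is read. The summary is descriptive, so no period or sequence term in a model would adjust for the imbalance. Sections 5.5 and 5.6 exclude sensitivity and additional analyses, so no other planned table would reveal it.

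**Working it through.** The SAP gives no adverse-event rate and no figure on this point, so there is nothing of the plan's own to reproduce. What can be computed is how much control exposure is open to the problem.

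**Inputs**
- Treatment period: 4 weeks (section 2.1).
- Washout: 3 weeks, between periods (section 2.1). It is used here as the post-dopamine window because it is the only such length in the SAP. That use is an assumption.
- Allocation 1:1 (section 2.2). Planned N = 20, revised to 12 (section 2.3).
- Gap g, in weeks, between end of titration and start of period 1: not given. Values of 0 and 1 are tried.
- The phase II safety population is all randomised patients who receive ICV dopamine or placebo (section 3.3); its size is not given. The 9 in section 2.3 is the number with complete primary-outcome data. It is used only to show the effect of an uneven split, with 4 or 5 patients in S-E assumed.

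**Where post-dopamine events go under the rule as written**
- E-S: titration, E1 (counted as dopamine), washout (not counted), S2 (counted as control).
- S-E: titration, S1 (counted as control), washout (not counted), E2 (counted as dopamine).

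**Share of control person-time within 3 weeks of ICV dopamine**

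Share = (3 − g) × n(S-E) / (4 × N)

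| N | n(S-E) | g = 0 | g = 1 |
|---|---|---|---|
| 20 | 10 | 30/80 = 37.5% | 20/80 = 25% |
| 12 | 6 | 18/48 = 37.5% | 12/48 = 25% |
| 9 | 4 | 12/36 = 33% | 8/36 = 22% |
| 9 | 5 | 15/36 = 42% | 10/36 = 28% |

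The share depends on the split between sequences and on the gap, not on N itself. With a gap of 3 weeks or more it is zero. In addition, 3 × 10 = 30 person-weeks of E-S washout (N = 20) lie outside both windows.

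**What that exposure could do to the comparison (illustration)**

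Let R be the true ratio of event rates, dopamine to control, and f the fraction of the dopamine excess that persists through the 3 weeks. With the 37.5% share, the observed ratio = R / (1 + f × 0.375 × (R − 1)).

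| f | R = 2 | R = 3 |
|---|---|---|
| 0 | 2.00 | 3.00 |
| 0.25 | 2/1.094 = 1.83 | 3/1.188 = 2.53 |
| 0.5 | 2/1.188 = 1.68 | 3/1.375 = 2.18 |
| 1 | 2/1.375 = 1.45 | 3/1.75 = 1.71 |

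R and f are assumed; the SAP supplies neither. With no carry-over there is no distortion.

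**The case against.** The strongest reply is that the problem rests on silence. The SAP describes the design briefly and leaves full detail of the phases and visits to the protocol, which is not shown and may set a gap before period 1. Table 1 allows V1 a delay of up to a week. A reader might infer that S-E control events are counted from the very day titration ends, but the SAP does not say so. This stands, and it is why the 37.5% is conditional.

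Other parts also have weight:
- A reader might infer that the comparison is biased, and always towards ICV dopamine. That needs persisting dopamine or withdrawal effects, for which the SAP gives no data. Residual benefit could instead suppress Parkinson-related events in S1 and work against ICV dopamine.
- A reader might take 33% to 42% as the share of misattributed events. It is a share of person-time, which also holds genuine control events, and its N = 9 is the efficacy count.
- Entry to phase II requires titration without complications. This limits events carried in, though not new events after ICV dopamine stops.
- The term treatment group is ambiguous, since sections 2.1 and 5.2.2 also call the sequences groups. If it means sequence, S1 and S2 are not pooled, but the dopamine-versus-control comparison in section 1.3 is then not produced. Neither reading resolves the matter.
- The summary is descriptive, in a small proof-of-concept study, so no error rate is affected.

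One part does not stand: that this is only a protocol detail. How events are assigned to treatments is for the SAP to settle, and its rule takes no account of what preceded each control period.

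**Conclusion.** The point holds as a gap in the adverse-event rule with a possible direction of bias. On the SAP's text, events soon after ICV dopamine stops would be placed under control in S-E and omitted in E-S. If dopamine or withdrawal effects cause such events, ICV dopamine would look better tolerated than it is. The control exposure concerned is at most 37.5% with equal sequences if period 1 follows titration directly, 25% with an assumed one-week gap, and none with 3 weeks or more. These figures rest on the 3-week washout as the relevant window and on no washout before period 1, since none is stated. They do not show that bias is present or how large it is. The consequence is confined to interpretation of the phase II tolerance objective; the primary efficacy analysis is not in question here.

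**What to change.** In section 5.2.2, replace the adverse-event sentence with the following.

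- Report phase II adverse events by sequence and period (E1, S1, washout, E2, S2), with events, patients and person-weeks for each.
- Show washout events under the preceding treatment or in a separate column, so that they are not lost.
- Do not rely on a single pooled control frequency.
- List for each event the time since last ICV dopamine. This also makes the actual interval between titration and period 1 visible.

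A display split at the plan's own 3-week washout length may be added as a supportive table. It should not be the main analysis. The cut-off has no stated basis for adverse events, and with equal sequences and no gap it would leave only 50 of 80 control person-weeks (N = 20) or 30 of 48 (N = 12) beyond 3 weeks.

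The cost is a change of wording, one extra table and one listing column, from event and infusion dates. Table 1 already records adverse events at every visit, and no treatment or visit changes. The downside is small cells, which should be read as counts rather than compared as rates.

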### 5.2.3 Long term follow-up

***Primary outcome:***

The percentage in "on" time without dyskinesia and with or without slight bradykinesia during a 7 day consecutive period (assessed using patient diary) between the last available follow-up and the evaluation during the treatment period of phase II part of DIVE will be done using a linear mixed model including phase (phase II vs. long term follow-up), and delay from phase II evaluation to long-term follow-up evaluation as fixed effects and patients as random effects to account the within intra-patients correlation. In cases of deviation to normality of model residuals, the difference between the phase II evaluation to long-term follow-up evaluation between the two evaluations by using a Wilcoxon-rank signed test.

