## **1.2 Research hypothesis**

The hypothesis of phase I trial is that, in Parkinson's disease in the stage of severe motor and non-motor complications related to L-dopa, the administration of intracerebroventricular dopamine is safe regarding the occurrence of serious adverse event. The hypothesis of phase II trial is that, in Parkinson's disease in the stage of severe motor and non-motor complications related to L-dopa, there is an increase in the Percent Time Over target (PTO) in the intervention phase (A-dopamine intracerebroventricular) by comparison to the control phase (usual optimized oral medical treatment). The hypothesis of long-term follow-up phase trial is the maintenance of efficacy on motor and non-motor complications.

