***Long term follow-up study:***

The primary objective is to assess the maintenance of efficacy of long-term continuous administration of intracerebroventricular dopamine on motor control and non-motor complications.

Secondary objectives are

- 1) To assess the maintenance of efficacy on:

- motor aspects
- cognitive-behavioural aspects: drowsiness, anxiety, depression, apathy, sleep, hallucinations
- cognition and psychiatric assessment
- quality of life
- general condition

- 2) To assess the maintenance of tolerance of intracerebroventricular dopamine administration

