#### **2.4 Framework**

Primary and secondary comparative objectives of phase II part of DIVE-1 trial are tested for superiority in favour of intervention versus control treatment period. For phase I study, none statistical tests will be done and only descriptive analysis with go no go rule for safety will be done. For long term follow-up phase, intra-patient comparisons will be done to assess the maintenance efficacy and safety.

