### **3 STATISTICAL PRINCIPLES**

#### **3.1 Confidence intervals and p-values**

All applicable statistical tests will be 2-sided and will be performed using a 5% significance level.

No statistical comparisons will be done for secondary objectives, only a descriptive analysis will be performed and we will report standardized differences between active and control period as effect sizes.

All confidence intervals (CIs) presented will be 95%CI and 2-sided.

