***Secondary outcomes:***

The same methods described to analyse the primary outcome of long-term follow-up phase will be used to analyse secondary and exploratory quantitative outcomes.

The frequency of adverse events from end of phase II trial to the last available follow-up will be reported.

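### The long-term phase sets out to show maintenance of efficacy, but its only planned comparison looks for a difference and has no margin or confidence-interval criterion, so no result of that test can establish maintenance.

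*SAP*

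**What the plan says.** Section 1.2 states: "The hypothesis of long-term follow-up phase trial is the maintenance of efficacy on motor and non-motor complications". Section 1.3 repeats it as the aim of the phase: "The primary objective is to assess the maintenance of efficacy of long-term continuous administration of intracerebroventricular dopamine on motor control and non-motor complications". A secondary objective is "To assess the maintenance of tolerance of intracerebroventricular dopamine administration". Section 2.4 names superiority as the framework for phase II, but for the long-term phase says only that "intra-patient comparisons will be done to assess the maintenance efficacy and safety".

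The primary outcome is diary based: the share of time spent on, free of dyskinesia and with at most slight bradykinesia (5.1.3). Section 5.2.3 sets the comparison "between the last available follow-up and the evaluation during the treatment period of phase II part of DIVE will be done" by a linear mixed model with phase and delay as fixed effects and patient as random effect. A Wilcoxon signed-rank test replaces it if the residuals depart from normality. Section 3.1 adds: "All applicable statistical tests will be 2-sided and will be performed using a 5% significance level". It also says that any confidence interval presented will be a two-sided 95% interval.

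For the other long-term outcomes, 5.2.3 says: "The same methods described to analyse the primary outcome of long-term follow-up phase will be used to analyse secondary and exploratory quantitative outcomes". The secondary outcomes listed in 5.1.3 include quantitative safety scales such as MDS-UPDRS part I, MOCA and NPI. Adverse events are only reported as frequencies.

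None of these sections states a margin, a tolerable loss or a rule for concluding maintenance. Sections 5.5 and 5.6 plan no sensitivity or additional analyses.

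**The concern.** To show maintenance is to show that no relevant loss has occurred since phase II. The planned test takes no change as its null hypothesis. Rejecting that null shows change; failing to reject it shows neither change nor its absence. The claim the phase wants to make is therefore the one statement this test cannot support.

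The incentive also runs the wrong way. Fewer patients and noisier diaries make a non-significant result more likely, whatever has happened to efficacy. Conversely, a small but consistent change could reach significance and look like failure. The same holds for the quantitative safety scales, if 5.2.3 is followed for them. At stake is the main long-term statement about an implanted treatment meant for continued use.

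**Working it through.** **Inputs.** Two-sided alpha 0.05 (SAP 3.1). From SAP 2.3: 10-point difference, SD 15, correlation 0.5, 20 patients planned, production cap of 12, and 9 patients with complete primary data. These planning values are for the phase II actimetry outcome (PTO). The SAP gives none for the diary outcome, so using them here is an assumption. The size of the long-term population is not stated; 9 to 12 is assumed, and the requirement of at least 6 months on ICV dopamine (3.3) could lower it.

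**The plan's own figure.** SD of the paired difference = 15 × √(2 × (1 − 0.5)) = 15. Standardised difference d = 10/15 = 0.667. With n = 20 the noncentrality is 0.667 × √20 = 2.98, and the two-sided paired t test has power 80.7%. The stated power above 80% is reproduced.

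**Probability of missing a true loss.** Paired t: miss = 1 − power, from the noncentral t with n − 1 degrees of freedom and noncentrality d√n. Exact Wilcoxon signed-rank: simulated with normal differences, so accurate to about one percentage point. The loss is expressed in SDs of the within-patient change.

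| True loss | t, n=9 | Wilcoxon, n=9 | t, n=12 | Wilcoxon, n=12 |
|---|---|---|---|---|
| 0.33 SD | 86% | 88% | 82% | 84% |
| 0.5 SD | 74% | 78% | 65% | 68% |
| 0.67 SD (10 points, SD 15) | 58% | 63-64% | 44% | 49% |
| 1 SD | 25% | 32% | 12% | 14-15% |

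**Sensitivity to the borrowed correlation.** For a 10-point loss with SD 15 at each visit, the paired t miss rate at n = 9 and n = 12 is 76% and 68% with correlation 0; 68% and 57% with 0.3; 58% and 44% with 0.5; 38% and 22.5% with 0.7.

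**Precision.** 95% CI half-width = t(0.975, n − 1) × 15/√n. At n = 9: 2.306 × 15/3 = 11.5 points. At n = 12: 2.201 × 15/3.464 = 9.5 points. At n = 9, an observed mean change of exactly zero would still leave a loss of more than 10 points inside the interval.

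**What a margin criterion would achieve.** Power to place the lower 95% limit above −m when there is no true change = 1 − F(t(0.975, n − 1)), where F is the noncentral t distribution function with noncentrality (m/15)√n. With m = 10, used only for illustration, the noncentrality is 2.00 at n = 9 and 2.31 at n = 12, and the power is 42% and 56%.

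**Limit of these figures.** They describe simple paired tests, not the mixed model with a delay term. If delay is coded as zero at phase II, the phase coefficient is the change extrapolated to zero delay. In simulations with assumed delays between 6 and 36 months, a 0.5 SD loss was then missed about 91-95% of the time.

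**The case against.** Four points on the other side have force.

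First, a reader might infer that the SAP will report p > 0.05 as maintenance. It does not say so; it states no rule at all. That reading is, however, the only way the test could support the hypothesis, which is why the SAP should exclude it.

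Second, a mixed model yields an estimated change, and 3.1 provides for 95% intervals, so a sound report is possible within the plan. That stands, but 5.2.3 does not tie the conclusion to an interval.

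Third, it is tempting to give one headline miss rate, or to say that a real decline would usually be missed. The documents support neither. The rate depends on an assumed loss, an assumed number of patients and a simplified test, and at 1 SD most losses would be detected.

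Fourth, it goes too far to say that tolerance is settled by a significance test. Adverse events are only described, and 3.1 rules out statistical comparisons for secondary objectives, of which tolerance is one. That rule conflicts with the instruction in 5.2.3 to use the primary method for secondary quantitative outcomes, so the status of the safety scales is unclear.

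The proof-of-concept setting and small numbers also argue against insisting on a margin, since a descriptive conclusion would be sound. None of this changes the mismatch between the primary objective and its test.

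**Conclusion.** The point holds for the long-term primary outcome: the stated aim is maintenance, and no outcome of the planned difference test can establish it. This follows from the logic of the test and needs no numerical assumption. It concerns the SAP text; whether the protocol sets a margin was not examined.

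The size does rest on assumptions. With 9 to 12 patients and a simple paired test, a true loss would be missed about 82-88% of the time at 0.33 SD of the within-patient change, 65-78% at 0.5 SD, 44-64% at 0.67 SD and 12-32% at 1 SD. For tolerance, the point reaches only the quantitative scales, and only if 5.2.3 prevails over 3.1. It should be fixed before the long-term data are analysed.

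**What to change.** In 5.2.3, base the conclusion on the estimated within-patient change, defined as last follow-up minus the phase II value under ICV dopamine, with its two-sided 95% CI. Use a Hodges-Lehmann interval if residuals are non-normal. State that p > 0.05 is not evidence of maintenance. Then choose one of two routes:

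- Fix and justify a maximum acceptable loss before the long-term data are analysed. Conclude maintenance only if the lower limit lies above minus that loss; otherwise report the result as inconclusive.
- Declare the phase descriptive and make no confirmatory maintenance claim.

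For secondary outcomes and quantitative safety scales, report the change with its 95% CI only, and reconcile the secondary-outcome paragraph of 5.2.3 with 3.1. The description of adverse events can stay as it is.

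The cost is SAP wording and, on the first route, one agreed margin. No new data are needed. The drawback of the first route is that a margin criterion will often be inconclusive at this size, as the 42% and 56% power figures show. The second route avoids this but gives up the confirmatory claim.

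### The long-term model leaves open how delay is coded and which coefficient measures maintenance; under one admissible coding, a steady loss of efficacy would not show in the phase effect

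*SAP*

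**What the plan says.** - **Objective (section 1.3, long-term follow-up).** The aim is "to assess the maintenance of efficacy of long-term continuous administration of intracerebroventricular dopamine on motor control and non-motor complications". Section 2.4 adds that "intra-patient comparisons will be done to assess the maintenance efficacy and safety".
- **Comparison (section 5.2.3, primary outcome).** The diary percentage is compared "between the last available follow-up and the evaluation during the treatment period of phase II part of DIVE", so each patient contributes two rows.
- **Model (same place).** The fixed effects are phase (phase II or long-term) and delay, with a random patient effect: "delay from phase II evaluation to long-term follow-up evaluation as fixed effects and patients as random effects". The text does not give delay's value on the phase II row, any centring or any interaction with phase.
- **Fallback (same place).** If the residuals are not normal, a signed-rank test is applied to the difference between the two evaluations, without delay.
- **Other long-term outcomes (section 5.2.3).** "The same methods described to analyse the primary outcome of long-term follow-up phase will be used to analyse secondary and exploratory quantitative outcomes".
- **Population and data.** Section 3.3 requires at least 6 months of ICV dopamine after phase II. Table 1 schedules the diary at each six-monthly long-term visit. Section 5.5 plans no sensitivity analyses.
- **A separate phase II point.** Section 2.4 states "Primary and secondary comparative objectives of phase II part of DIVE-1 trial are tested for superiority". Section 3.1 states "No statistical comparisons will be done for secondary objectives", and section 5.2.2 makes these outcomes descriptive.

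**The concern.** With two rows per patient, phase and time since phase II are nearly the same variable. Entering both as main effects splits the change between them, and the split depends on how delay is coded. The SAP fixes neither the coding nor the coefficient to be read. One coding leaves the delay term with no influence on the phase contrast. The other makes the phase coefficient answer a question about a time at which nobody is observed. Maintenance is the long-term primary objective, so an analyst who chose the second coding and read the phase coefficient could overlook a real, gradual loss. The same uncertainty carries over to every long-term outcome analysed by the same method.

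**Working it through.** **The plan's own figure.** The SAP gives no design figure for the long-term phase. The only one is in section 2.3 for PTO in phase II: SD 15, correlation 0.5, difference 10, n = 20, power above 80%. The SD of a paired difference is 15 × √(2 × (1 − 0.5)) = 15. A paired t-test at two-sided 5% then has power 0.807, so the figure reproduces. The SD of 15 is borrowed below for the diary outcome, as an assumption.

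**Algebra.** Write y = b0 + b1·phase + b2·delay + patient effect + error, and let D be the follow-up value minus the phase II value.

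- *Coding A, the same delay t on both rows.* The delay term cancels: D = b1 + error. The estimate of b1 is the mean of D. In 300 mixed-model fits the largest gap from the mean of D was 4 × 10⁻¹⁴.
- *Coding B, delay 0 at phase II and t at follow-up.* D = b1 + b2·t + error, so b1 is the change at t = 0. If the true loss is steady, D = −s·t on average, then b1 = 0 and b2 = −s. The whole loss sits in b2.

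**Precision under coding B.** From the regression of D on t, the SE of b1 exceeds that of the mean of D by a factor √(1 + n·t̄²/Sxx). For 9 evenly spaced delays:

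- 6 to 36 months: spacing 3.75, Sxx = 3.75² × 60 = 843.75, n·t̄² = 9 × 21² = 3969, factor √(1 + 4.70) = 2.4.
- 12 to 24 months: spacing 1.5, Sxx = 1.5² × 60 = 135, n·t̄² = 9 × 18² = 2916, factor √(1 + 21.6) = 4.8.

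**Simulation.** Assumed: 9 patients (the number with complete phase II primary data, section 2.3), SD of D = 15, uniform delays, loss of 1 point per month, 10,000 runs per row, two-sided 5%. Under coding B, phase is the intercept of D regressed on delay.

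| Delays (months) | True mean loss | A: mean phase effect, significant | B: mean phase effect (SD), significant | B: delay slope significant |
|---|---|---|---|---|
| 6–12 | 9 | −9.0, 36% | 0.0 (30), 5.1% | 6.2% |
| 12–24 | 18 | −18.0, 86% | −0.5 (30), 5.1% | 8.6% |
| 6–36 | 21 | −20.9, 88.5% | +0.2 (14.9), 5.6% | 30% |

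At 0.5 point per month and delays of 6–36 months, A gives −10.5 (43% significant) and B gives +0.2 (4.9%). A second setting (8 patients, 6–30 months, residual SD 8, 1 point per month) gives a true mean loss of 18. Phase under B then averages about 0 and is significant in 5%, while the unadjusted change is significant in about 90–92%.

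**Check against the mixed model itself.** The random-intercept model also uses between-patient information, so in a single data set its coding B estimate need not equal the regression intercept. On average they agree: over 300 mixed-model fits with delays of 6–36 months, phase under B averaged −0.1 (SD 14.7). The large-sample Wald test rejected in 9.3% of those fits. That is above nominal at this sample size, but far below the 88.5% for the paired change.

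**Fallback.** The signed-rank test addresses the change at the observed delays. Under A this is broadly the same target as the phase effect. Under B the residual check would switch the test from the change at delay 0 to the change at the observed delays.

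**The case against.** The strongest reply is that the wording describes one interval per patient, which is coding A. The paired signed-rank fallback points the same way. On that reading the phase effect is the plain mean change, a steady loss stays visible, and the only defect is an adjustment that does nothing for the phase contrast. This is the more natural reading, and it stands as a limit on the point. It does not settle the matter, because in a long-format data set with one row per evaluation, an analyst can as readily enter time since phase II, which is coding B.

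Two further replies also stand. The SAP nowhere says that a non-significant result proves maintenance; the fair criticism is that it gives no criterion. Comparing only the last visit is a legitimate simple choice for about nine patients, although it leaves scheduled diary data unused.

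A reader might also infer that section 5.2.3 contradicts section 3.1 by testing long-term secondary outcomes. The text does not support this. The sentence in 3.1 goes on to effect sizes between an active and a control period, and the long-term phase has no control period. The revision history ties the move to descriptive analysis to phase II, and section 2.4 separately plans within-patient comparisons for the long-term phase. A family-wise error figure that treats the long-term outcomes as independent would not hold either, because several diary outcomes overlap or are nested.

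**Conclusion.** The point holds as a specification gap with a real consequence. Neither coding delivers a delay-adjusted change: under A delay has no effect on the phase contrast, and under B the phase effect refers to delay 0, outside the follow-up data. Under B, a steady loss averaging 9 to 21 points would leave the phase effect near zero and non-significant in about 95% of trials, and the delay slope would reveal it in at most about 30% of trials in the 9-patient scenarios. These sizes rest on assumed values for patient number, SD, delays and rate of loss. An abrupt early loss would still enter the phase effect, though imprecisely.

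A reader might infer that the planned model is biased toward no change whatever the coding. That is not so, since under A the loss is estimated without distortion. The phase II primary test is untouched, and the June 2024 analysis in section 2.6 is for phase II. The gap should be fixed before the long-term data are modelled. The disagreement between section 2.4 and sections 3.1 and 5.2.2 about phase II secondary objectives is real but separate.

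**What to change.** In section 5.2.3, define the estimand as the change from the phase II dopamine evaluation, either at the observed mean delay or at stated times such as 6 and 12 months. Then specify one of these models:

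1. Two rows per patient, with phase and phase × (delay minus mean delay), and a random patient effect. The phase coefficient is then the change at the mean delay, and the interaction describes how the change varies with delay. This keeps the phase effect and the signed-rank fallback on broadly the same target.
2. All six-monthly diary visits, with time since the phase II dopamine evaluation as the only time term and a random patient effect, reporting the change at the stated times. This uses data already scheduled. A linear time term assumes gradual change, so option 1 is safer if an early step is plausible.

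Name the coefficient or contrast that answers the objective, report it with a 95% CI, and say in advance how that CI supports a statement on maintenance. Carry the same definition to the other long-term outcomes.

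The cost is SAP wording and modest programming, with no new data. Precision will be limited: with 9 patients and an SD of change of 15, the 95% CI half-width for the mean change is 2.306 × 15/√9 = 11.5 points.

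Separately, amend section 2.4 so that it agrees with sections 3.1 and 5.2.2 that phase II secondary objectives are described and not tested.
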